1 INTRODUCTION AND BACKGROUND INFORMATION

2.1 Study Design

This is an open-label, multicenter, 4-stage study consisting of an optimization/stabilization period (Stage 1), a 24-week treatment period in which all subjects will receive teduglutide 0.05 mg/kg/day (Stage 2), and a long-term extension (Stages 3 and 4).

At least 5 subjects may be enrolled during the recruitment period, which ends approximately 6 months after the initiation of the study.

Main Treatment Period (Stages 1 and 2)

Stage 1 will include a screening visit; a maximum 8-week PN/I.V. optimization period (if required); and a stabilization period that demonstrates stable PN/I.V. support for a minimum of 4 weeks to a maximum of 8 weeks.

If at screening a subject does not have a stable PN/I.V. volume, defined as a 48-hour urine output within 2 to 4 L, he/she will enter the optimization period, during which the minimally tolerated stable PN/I.V. volume will be determined during a period of up to 8 weeks. If it is not possible to keep the subject adequately hydrated and nourished within the target urine output range, the minimally tolerated PN/I.V. volume will be documented.

All subjects will then enter the stabilization period, during which the target volume will be maintained for at least 4 consecutive weeks (8 weeks maximum) prior to entering the dosing period (Stage 2).

If a subject fails to maintain a stable PN/I.V. volume for at least 4 consecutive weeks, the subject may start the optimization period again, beginning with Week 2 (Visit 1.1). Those subjects who fail to stabilize after 2 attempts will not proceed further and will not be included in Stage 2.

Stage 2 will be a 24-week dosing period, during which subjects will self-administer teduglutide 0.05 mg/kg/day at home. Stage 2 will begin with baseline assessments of hydration and nutritional status once the subjects have demonstrated PN/I.V. stability for 4 to 8 weeks. At least 5 subjects will be enrolled. The on-treatment study visits will occur at Weeks 2, 4, 8, 12, 16 and 20, with the last scheduled visit at Week 24 of Stage 2.

Extension Treatment Period (Stages 3 and 4)

[figure not shown]

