Stages 3 and 4 constitute the long-term extension portion of the study. Stage 3, which will begin immediately following Stage 2, will include subjects who complete the main treatment period and who are willing to continue with treatment teduglutide 0.05 mg/kg/day SC for up to an additional 24 months. In Stage 4, which will begin immediately following Stage 3, subjects will continue treatment with teduglutide 0.05 mg/kg/day SC in Study TED-C14-004 until teduglutide is commercially available for each subject, the subject's participation in this study is discontinued, or the study is discontinued.

Any subject who achieves complete independence from PN/I.V. support at any time during the Stages 2, 3 or 4 treatment periods will continue to receive teduglutide treatment. If a subject relapses following achievement of PN/I.V. independence, PN/I.V. support will be re-initiated and the subject will continue receiving teduglutide.

A schematic representation of the study design is displayed in [Figure 1](#).

The Schedule of Evaluations and Procedures for each stage are outlined in Section 6.4 of the protocol.

Figure 1 Study Diagram

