13.2 Adverse Events

Adverse events will be summarized in three categories: 1) Overall TEAEs that happened in the study, 2) TEAEs that happened in Stage 2, and 3) TEAEs that happened in Stage 3 and 4. AEs will be coded using the MedDRA. Investigator verbatim as well as preferred terms and body systems will be included in the listings, and the corresponding list of body systems, preferred terms and the verbatim terms that code to each preferred term will be presented as a preface to the listings of the AEs.

Treatment emergent AEs (TEAEs) are defined as AEs whose onset occurs, severity worsens, or intensity increases after receiving the study medication. AEs with an unknown date of onset and a stop date after the start of the study period or unknown will be included as treatment emergent AEs. Any AE with a start date equal to the date of first dose, where the time of the AE can't definitively place the start of the AE prior to the first dose, will be considered treatment emergent. If any AE records contain only partial dates, these will be handled by imputation, as described in Section 6.3. AEs which are not treatment emergent will be flagged in listings.

AEs will be summarized overall using descriptive statistics (e.g., number and percent of subjects). The number of events will also be presented except for summaries by highest category. Categories summarized will include any TEAEs, severity of TEAEs (any and highest category), investigator assessment of relationship of TEAEs to study treatment, treatment emergent serious AEs (TESAEs), severity of TESAEs, investigator assessment of relationship of TESAEs to study treatment, TEAEs leading to death, and TEAEs leading to discontinuation.

Treatment emergent AEs will be summarized using number and percentage of subjects. Subject incidence for AEs within each SOC and PT will be presented, unless otherwise specified. TEAEs will be summarized by Severity. The number of events will also be summarized except for summaries by highest category. TEAEs will be summarized by relationship to the drug, whether it is related or not related. TESAEs will be summarized. TESAE will also be summarized based on Severity as well as Relationship. Presentation by SOC and PT will present SOC sorted alphabetically and PT within SOC by descending incidence.

Summaries of TEAEs, related TEAEs, and TESAEs will also be presented by PT. These presentations will be sorted by descending incidence.

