Listings will be provided for serious adverse events (SAEs), AEs leading to death, and AEs leading to discontinuation of study drug. The listings will be sorted by subject identifier and will include gender, age, SOC, PT, reported term, start date/time, end date/time, frequency, severity, relationship, action taken, and outcome.

Pre-Treatment AEs will be summarized. These AEs will be summarized using number and percentage of subjects. Subject incidence for AEs within each SOC and PT will be presented. The number of events will also be summarized. Presentation by SOC and PT will present SOC sorted alphabetically and PT within SOC by descending incidence.

TEAEs will be summarized by time to onset (<6 months, 6 – <12 months, 12 – <24 months, 24 – <30 months, >=30 months). These AEs will be summarized using number and percentage of subjects. Subject incidence for AEs within each SOC and PT will be presented. The number of events will also be summarized. Presentation by SOC and PT will present SOC sorted alphabetically and PT within SOC by descending incidence.

One of the benefits of Teduglutide's ability to reduce PN assumption is to reduce or eliminate the risk of systemic catheter-related infections in SBS patients who are PN dependent. Adverse events that are considered to be central line systemic infections include central line infection, catheter related infection, catheter sepsis, catheter bacteraemia,

bacteraemia, and blood culture positive. These TEAEs will be presented by PT, sorted by descending incidence.

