| Table 14.3.2.13.1 | Details of Adverse Events Leading to Discontinuation - Stage 2 Only | Safety Population |
| Table 14.3.2.13.2 | Details of Adverse Events Leading to Discontinuation - Stage 3 and 4 Only | Safety Population |
| Table 14.3.2.14 | Details of Adverse Events Leading to Death | Safety Population |
| Table 14.3.2.14.1 | Details of Adverse Events Leading to Death - Stage 2 | Safety Population |
| Table 14.3.2.14.2 | Details of Adverse Events Leading to Death - Stage 3 and 4 Only | Safety Population |
| Table 14.3.2.15 | Summary to Treatment Emergent Adverse Events by Time to Onset, System Organ Class, and Preferred Term | Safety Population |
| Table 14.3.2.16 | Summary of Pre-treatment Adverse Events by System Organ Class and Preferred Term | Safety Population |
| Table 14.3.2.17 | Summary of Treatment Emergent Central Line Systemic Infections by Preferred Term | Safety Population |
| Table 14.3.2.17.1 | Summary of Treatment Emergent Central Line Systemic Infections by Preferred Term - Stage 2 Only | Safety Population |
| Table 14.3.2.17.2 | Summary of Treatment Emergent Central Line Systemic Infections by Preferred Term - Stage 3 and 4 Only | Safety Population |
| Table 14.3.3.1 | Summary of Laboratory Values and Change from Baseline by Visit - Chemistry | Safety Population |
| Table 14.3.3.2 | Summary of Laboratory Values and Change from Baseline by Visit - Hematology | Safety Population |
| Table 14.3.3.3 | Summary of Laboratory Values and Change from Baseline by Visit - Urinalysis | Safety Population |
| Table 14.3.3.4 | Summary of Antibody Results by Visit | Safety Population |
| Table 14.3.3.5 | Shift from Baseline to Post-baseline in Clinical Laboratory Parameters by Visit - Chemistry | Safety Population |
| Table 14.3.3.6 | Shift from Baseline to Post-baseline in Clinical Laboratory Parameters by Visit - Hematology | Safety Population |
| Table 14.3.3.7 | Shift from Baseline to Post-baseline in Clinical Laboratory Parameters by Visit - Urinalysis | Safety Population |
| Table 14.3.3.8 | Summary of Post-Baseline Markedly Abnormal Laboratory Values – Chemistry | Safety Population |
| Table 14.3.3.9 | Summary of Post-Baseline Markedly Abnormal Laboratory Values – Hematology | Safety Population |
| Table 14.3.4.1 | Change and Percent Change in 48-hour Fluid Intake from Baseline by Visit | Safety Population |
| Table 14.3.4.2 | Change and Percent Change in 48-hour Urine Output from Baseline by Visit | Safety Population |

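### The central line infection tables give subject percentages and event counts over stages of very unequal length, with no time-at-risk denominator

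*SAP*

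**What the plan says.** SAP Section 13.2 gives the reason for this summary: through lower PN use, teduglutide may "reduce or eliminate the risk of systemic catheter-related infections in SBS patients who are PN dependent". It lists the terms that count as central line systemic infections and sets the layout: "These TEAEs will be presented by PT, sorted by descending incidence".

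The measures come from the general rule in the same section: "Treatment emergent AEs will be summarized using number and percentage of subjects". That section also plans the number of events, except in summaries by highest category. Adverse events are shown overall and by stage: "2) TEAEs that happened in Stage 2, and 3) TEAEs that happened in Stage 3 and 4".

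Section 16.1 lists an overall infection table (14.3.2.17) and two stage tables:
- 14.3.2.17.1: "Summary of Treatment Emergent Central Line Systemic Infections by Preferred Term - Stage 2 Only"
- 14.3.2.17.2: "Summary of Treatment Emergent Central Line Systemic Infections by Preferred Term - Stage 3 and 4 Only"

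On duration, Section 2.1 states: "Stage 2 will be a 24-week dosing period". Stage 3 continues treatment "for up to an additional 24 months". Stage 4 has no fixed end.

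Neither Section 13.2 nor the table list mentions person-time or an event rate.

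**The concern.** Risk is a matter of events relative to time at risk. These tables are introduced by a statement about risk, but they report two measures that increase with observation time even when the underlying rate is constant. The two stage tables cover very different lengths of time and will appear next to each other in the report. A reader who has just been told that treatment may lower infection risk will naturally look from one to the other. A real fall in the rate could then look like a rise. If follow-up after Stage 2 turned out short, an unchanged rate could look like a fall.

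**Working it through.** The SAP states no infection rate, and its sample size rests on feasibility, so there is no planned figure to reproduce. The check is person-time arithmetic.

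**Inputs from the SAP (Section 2.1)**
- Stage 2: 24 weeks = 168/365.25 = 0.460 years.
- Stage 3: at most 24 months = 2 years, or 104.4 weeks.
- Stage 4: open-ended.
- Subjects: at least 5.

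**Assumptions**
- Stage 2 infection rate of 0.25 to 2 per subject-year.
- Constant rate within a stage, and the same subjects in both periods.
- Full 24 months in Stage 3 and no Stage 4 time, unless stated otherwise.

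**Length ratio.** 2/0.460 = 4.35. With an assumed 6 or 12 months of Stage 4, it is 2.5/0.460 = 5.4 or 3/0.460 = 6.5.

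**Break-even.** Expected events = subjects × rate × time. The later count exceeds the Stage 2 count unless the rate falls by more than 1 − T(Stage 2)/T(Stages 3 and 4):
- Stage 3 only: 1 − 0.460/2 = 77%
- plus 6 months of Stage 4: 1 − 0.460/2.5 = 82%
- plus 12 months of Stage 4: 1 − 0.460/3 = 85%

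The expected share of subjects with at least one event is 1 − exp(−rate × time). It depends on the same product, so its break-even point is the same. The break-even does not depend on the assumed rate.

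**A rate that halves after Stage 2**

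| Stage 2 rate per subject-year | Subjects affected, Stage 2 | Subjects affected, Stage 3 | Expected events in 5 subjects |
|---|---|---|---|
| 0.25 | 10.9% | 22.1% | 0.57 to 1.25 |
| 0.5 | 20.5% | 39.3% | 1.15 to 2.50 |
| 1 | 36.9% | 63.2% | 2.30 to 5.00 |
| 2 | 60.1% | 86.5% | 4.60 to 10.00 |

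At 1 per year, a 75% fall still shows as 36.9% to 39.3%. A 90% fall shows as a decrease, 36.9% to 18.1%.

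**Sensitivity to follow-up.** If mean Stage 3 and 4 follow-up were 1 year, the break-even fall is 1 − 0.460/1 = 54%. At 0.5 years it is 1 − 0.460/0.5 = 8%. At 0.46 years (24 weeks) the distortion is nil. Below that it reverses: at 0.25 years, an unchanged rate gives 0.25/0.460 = 54% of the Stage 2 count.

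**With a denominator.** Take 5 subjects, 1 per year, halved in Stage 3. Stage 2 has 5 × 0.460 = 2.30 subject-years and 2.30 expected events, so 1.0 per subject-year. Stage 3 has 10 subject-years and 5.0 expected events, so 0.5. The halving is then visible.

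**The case against.** **The plan promises no demonstration.** A reader might infer that the tables are offered as evidence of benefit, or that the stages are to be compared. The SAP says neither. It gives one background sentence, a term list and a sort order. The stage split is the layout used for most adverse event tables. Section 6.1 discourages inferential statistics, Section 6.6 plans no testing, and the comparison with the Phase 3 study has been dropped. This stands. The point is therefore about how the tables will be read, not about a flawed test.

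**Event counts are already planned.** A reader of the infection paragraph alone might conclude that only the percentage of subjects will be shown. The general rule in Section 13.2 adds the number of events. This stands too, but counts without time have the same length problem.

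**Other outputs show timing.** Table 14.3.2.15 gives events by time to onset, including two equal 6-month periods, and listings show every event. With about 5 subjects this helps. However, the later periods in that table are unequal, it carries no person-time, and it does not group the central line terms. Extent of exposure (Section 13.1) runs from first to last dose and is not used as a denominator. The table shells are in a separate file that is not shown, so a rate column there cannot be excluded.

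**The size is hypothetical.** No rate is given and 24 months is a maximum. With 5 subjects each person is 20 percentage points, so 37% against 63% is about 2 against 3 subjects. This limits the magnitude. The direction holds whenever mean later follow-up exceeds 24 weeks.

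**Rates would not show a treatment effect.** Correct. All stages are on treatment, there is no control, and Stage 3 takes only Stage 2 completers willing to continue. Rates remove the length artefact and nothing more.

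**Conclusion.** The point holds as a cheap improvement to three descriptive tables. The planned measures cannot be read across stages as a statement about risk. With a full 24-month Stage 3, the infection rate would have to fall by more than about 77% before the expected event count in the same subjects fell. That figure follows from the stage lengths. It assumes a constant rate within each stage and complete follow-up. The percentages in the table above rest additionally on assumed infection rates.

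The documents do not support the stronger conclusion that the report will show a misleading rise. That depends on actual follow-up, and early drop-out could shrink or reverse the distortion. Nor do they support saying that the SAP claims to prove reduced risk from these tables.

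**What to change.** In Tables 14.3.2.17, 14.3.2.17.1 and 14.3.2.17.2, add two columns beside the planned counts and percentages: total subject-years on treatment within the period covered by the table, and events per subject-year. Footnote the two stage tables to say that percentages from stages of different length are not comparable. Also state there or in Section 13.2 that the stage rates are descriptive and are not evidence of a treatment effect.

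Do not make a rate per PN/IV day the main measure. The stated benefit works through less PN use: if PN days and infections both halve, that ratio is unchanged and the benefit disappears from view. Full PN-day totals are also not assured, because Section 11.1 uses diary volumes only from the 14 days before each scheduled visit.

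The cost is small. Dose dates and adverse event start dates are already collected, and the stage-specific tables already need a date that separates Stage 2 from Stage 3. The downside is that rates from about 5 subjects will be unstable, so the event counts and subject-years must stay visible next to them.

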13.3 Clinical Laboratory Evaluation

Laboratory parameters will be collected and processed via a central laboratory, SRL, and presented in standard international (SI) units. Clinical laboratory evaluations include the following:

- Chemistry
 - Alanine Aminotransferase
 - Albumin
 - Alkaline Phosphatase
 - Amylase
 - Aspartate Aminotransferase
 - Total Bilirubin
 - Direct Bilirubin
 - Indirect Bilirubin
 - Blood Urea Nitrogen
 - C Reactive Protein
 - Calcium
 - Chloride
 - Total Cholesterol
 - Creatinine
 - Creatinine Clearance
 - Gamma Glutamyl Transferase
 - Glucose
 - Lipase
 - Magnesium
 - Phosphate
 - Potassium
 - Sodium
 - Triglycerides
 - Uric Acid

- Hematology
 - Erythrocytes
 - Hematocrit
 - Hemoglobin

- Leukocytes
- Platelets
- Urinalysis
 - Urine Blood
 - Urine Glucose
 - Urine Leukocytes
 - Urine Microscopic
 - pH
 - Urine Osmolality
 - Urine Protein
 - Urine Sodium

Quantitative results will be summarized for hematology, serum chemistry, and selected urinalysis parameters at each visit collected and at endpoint. Both actual values and change from baseline will be summarized with descriptive statistics defined in Section 6.1.

Additionally, shift tables will be presented for parameters provided by the central laboratory, summarizing cross tabulations of low, normal, and high based on the parameter normal range, from baseline to Week 24, End of Stage 3 and End of Stage 4. Percentages for shift tables will be based on the number of subjects with a value at baseline and at least one post-baseline visit.

Markedly abnormal laboratory values are defined in Table 3. These criteria are based on lab normal ranges and discussions with the experts. The number and percentage of subjects with post-baseline results qualifying as markedly abnormal as defined in this table will be summarized by parameter. A listing will present all values for a subject and laboratory parameter if at least one post-baseline value for that subject and parameter is markedly abnormal.

Table 3 Markedly Abnormal Laboratory Criteria

| Lab parameter | Unit | Lower Limit | Upper Limit |
|----------------------|--------|-------------|-------------|
| Chemistry | | | |
| Albumin | g/L | <=20 | >=90 |
| Alkaline Phosphatase | U/L | NA | >2*ULN |
| ALT | U/L | NA | >3*ULN |
| Amylase | U/L | <=15 | >=350 |
| AST | U/L | NA | >3*ULN |
| Bilirubin (total) | µmol/L | NA | >2*ULN |
| BUN | mmol/L | NA | >=10.7 |
| Calcium (total) | mmol/L | <=2.1 | >=3.0 |
| Chloride | mmol/L | <=80 | >=125 |

| | | | |
|----------------------------|--------------------|------------------------------------|----------------------------------|
| Cholesterol (total) | mmol/L | NA | >=12.9 |
| Creatinine | µmol/L | NA | >=177 |
| C Reactive Protein | mg/L | NA | >21 |
| Glucose | mmol/L | <=1.7 | >=13.9 |
| Gamma glutamyl transferase | U/L | NA | >=100 |
| Lipase | U/L | NA | >3*ULN |
| Magnesium | mmol/L | <LLN | >ULN |
| Phosphate | mmol/L | NA | >=2.0 |
| Potassium | mmol/L | <=2.5 | >=6.5 |
| Sodium | mmol/L | <=120 | >=165 |
| Triglycerides | mmol/L | NA | >=5.6 |
| Uric acid | µmol/L | NA | >=624 (males) >=505 (females) |
| Hematology | | | |
| Hematocrit | L/L | <=0.37 (males) <=0.32 (females) | >0.54 (males) NA (females) |
| Hemoglobin | g/L | <=115 (males) <=95 (females) | NA |
| Platelets | 10 ⁹ /L | <=75 | >=700 |

Laboratory results will be presented in an appendix data listing for each lab panel (chemistry, hematology, urinalysis) by subject, visit, and parameter. Laboratory values outside of the normal range will be flagged. Categorical urinalysis findings and urine pregnancy results will be presented in appendix data listings only.

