For summarizations of categorical data, an Unknown or Missing category should be added to any variable for which information is not available for all subjects. However, only the number of unknown or missing subjects will be presented, and percent will be based on non-missing data.

Individual data listings will be sorted and presented by subject number and visit date.

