| Table 14.2.2.4 | Binary Response Status by Visit Based on Investigator Prescribed Data | Per-Protocol Population |
| Table 14.2.3.1 | Change and Percent Change in PN Volume from | Intention-to-Treat Population |

| | | |
|------------------|---|-------------------------------|
| | Baseline by Visit Based on Subject Diary Data | |
| Table 14.2.3.2 | Change and Percent Change in PN Volume from Baseline by Visit Based on Subject Diary Data | Per-Protocol Population |
| Table 14.2.3.3 | Change and Percent Change in PN Volume from Baseline by Visit Based on Investigator Prescribed Data | Intention-to-Treat Population |
| Table 14.2.3.4 | Change and Percent Change in PN Volume from Baseline by Visit Based on Investigator Prescribed Data | Per-Protocol Population |
| Table 14.2.4.1 | Change and Percent Change in Number of Days of PN Usage from Baseline by Visit Based on Investigator Prescribed Data | Intention-to-Treat Population |
| Table 14.2.4.2 | Change and Percent Change in Number of Days of PN Usage from Baseline by Visit Based on Investigator Prescribed Data | Per-Protocol Population |
| Table 14.2.5 | Number (%) of Subjects Who Stop PN Usage Based on Prescribed and Subject Diary Data | Intention-to-Treat Population |
| Table 14.2.6 | Change and Percent Change in PN Kilocalories from Baseline by Visit | Intention-to-Treat Population |
| Table 14.2.7 | Change and Percent Change in Citrulline from Baseline by Visit | Intention-to-Treat Population |
| Table 14.3.1.1 | Extent of Exposure | Intention-to-Treat Population |
| Table 14.3.1.2 | Extent of Exposure | Safety Population |
| Table 14.3.2.1 | Overall Summary of Treatment Emergent Adverse Events | Safety Population |
| Table 14.3.2.1.1 | Overall Summary of Treatment Emergent Adverse Events - Stage 2 Only | Safety Population |
| Table 14.3.2.1.2 | Overall Summary of Treatment Emergent Adverse Events - Stage 3 and 4 Only | Safety Population |
| Table 14.3.2.2 | Summary of Treatment Emergent Adverse Events by System Organ Class and Preferred Term | Safety Population |
| Table 14.3.2.2.1 | Summary of Treatment Emergent Adverse Events by System Organ Class and Preferred Term - Stage 2 Only | Safety Population |
| Table 14.3.2.2.2 | Summary of Treatment Emergent Adverse Events by System Organ Class and Preferred Term - Stage 3 and 4 Only | Safety Population |
| Table 14.3.2.2.3 | Summary of Treatment Emergent Adverse Events by System Organ Class and Preferred Term - Stage 3 Only | Safety Population |

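### Shift-table percentages count subjects with no value at the tabulated time point, and the Stage 3/4 and time-to-onset adverse event tables have no denominator matched to those observed

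*SAP*

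**What the plan says.** **Shift tables.** Section 13.3 cross-tabulates low, normal and high results "from baseline to Week 24, End of Stage 3 and End of Stage 4". It then sets one denominator for all three time points: "Percentages for shift tables will be based on the number of subjects with a value at baseline and at least one post-baseline visit". Section 15.2 has a different general rule for categorical data. Where information is lacking for some subjects, "only the number of unknown or missing subjects will be presented, and percent will be based on non-missing data".

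**Stage-specific adverse events.** Section 16.1 lists tables such as "Summary of Treatment Emergent Adverse Events by System Organ Class and Preferred Term - Stage 3 and 4 Only", and some for Stage 3 alone and Stage 4 alone. All are labelled Safety Population. Section 7.2 defines that set as every ITT subject dosed at least once, whatever stage was reached. Section 2.1 admits to Stage 3 only Stage 2 completers who agree to go on. The SAP defines no Stage 3 or Stage 4 analysis set.

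**Time to onset.** Section 13.2 says "TEAEs will be summarized by time to onset", in five intervals from under 6 months to 30 months or more, and adds: "These AEs will be summarized using number and percentage of subjects". It gives no denominator. Section 16.1 labels this table Safety Population too.

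**The concern.** A percentage at a given time should rest on the subjects who could have contributed to it at that time. The shift rule breaks this by its own wording. A subject with only baseline and Week 2 values belongs to the End of Stage 4 denominator but to no cell of that table. Because Section 15.2 points the other way, two programmers could follow the SAP and report different percentages from the same data.

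The adverse event tables raise a related question. If the label Safety Population also sets the column N, a subject who never entered Stage 3 is counted as one who had no event in Stages 3 and 4. The same holds for a subject whose observation ended before a later onset interval began. Section 2.2 gives safety as one purpose of the extension, and these are its main safety tables. With a minimum enrolment of 5, one subject more or less in the denominator moves a percentage visibly.

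**Working it through.** The SAP states no rate or attrition figure on this point, so there is no figure of its own to reproduce.

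**1. The two shift rules side by side**

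| Subject's data | Section 13.3 denominator, End of Stage 4 | Section 15.2 denominator | Fills a cell? |
|---|---|---|---|
| Baseline and End of Stage 4 | counted | counted | yes |
| Baseline and Week 2 only | counted | not counted | no |

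The rules agree only if every subject with a baseline value and any post-baseline visit also has a value at the tabulated time point.

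**2. Effect on the shift cells**

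Let N be the Section 13.3 denominator, m the number with a value at the time point and x the count in a cell.

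- As written: 100x/N. Among those observed: 100x/m. Ratio: m/N, the same for every cell.
- Sum of all cells as written: 100m/N.

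Assume N = 5 and m = 3, with two subjects normal to normal and one normal to high. As written, the cells are 2/5 = 40.0% and 1/5 = 20.0%, which sum to 60.0%. Among those observed they are 2/3 = 66.7% and 1/3 = 33.3%, which sum to 100%.

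**3. Effect on Stage 3/4 adverse event incidence, if N is the full Safety Population**

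The same formula applies, with m the number who entered the stage. The value N = 5 is the minimum in Section 2.1. The values 7 and 10, and every m, are assumptions. One subject is affected.

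| N | 100/N | m | 100/m | m/N |
|---|---|---|---|---|
| 5 | 20.0% | 5 | 20.0% | 1.00 |
| 5 | 20.0% | 4 | 25.0% | 0.80 |
| 5 | 20.0% | 3 | 33.3% | 0.60 |
| 5 | 20.0% | 2 | 50.0% | 0.40 |
| 7 | 14.3% | 6 | 16.7% | 0.86 |
| 7 | 14.3% | 5 | 20.0% | 0.71 |
| 10 | 10.0% | 9 | 11.1% | 0.90 |
| 10 | 10.0% | 7 | 14.3% | 0.70 |

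**4. Time to onset**

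Stage 2 lasts 24 weeks: 168 days / 30.4 = about 5.5 months. Stage 3 adds up to 24 months, which gives about 29.5 months. On treatment, the last interval (30 months or more) is therefore reached essentially only in Stage 4. Section 2.1 lets the length of Stage 4 vary by subject. The number observed in the late intervals can thus differ from the Safety Population N, and no such number is planned for the table.

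**The case against.** The adverse event denominators are inferred. Section 13.2 asks for numbers and percentages and names no N, Section 16.1 gives a population label and not a column N, and the table shells are in a separate file that could use N per stage. Crude incidence by period on a fixed safety set is also an accepted descriptive convention if labelled as such. This stands. For these tables the sound criticism is that the denominator is not fixed and no stage or at-risk set is defined, and the m/N effect depends on the natural reading of the label.

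A reader might go further and infer that late-phase safety rates are understated, or that the shift tables hide abnormal results. The documents support neither. Understatement needs subjects to leave, and the SAP gives no attrition figure. In the shift tables normal-to-normal shrinks by the same factor as every other cell.

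The harm is also limited. Event counts accompany the system organ class and onset tables, disposition is tabulated by stage (Section 8.4), exposure is tabulated in the same month intervals as onset (Section 13.1), and subject listings are planned (Section 16.3). A reader could approximate the numbers at risk, but that does not settle which percentage the tables will print.

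The unequal interval widths are no fault, since they match the exposure table. One caution bears on the remedy: the treatment-emergent definition in Section 13.2 has no cutoff after the last dose. Counting only subjects still on treatment could leave a post-treatment event in the numerator while its subject is absent from the denominator.

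**Conclusion.** The shift-table point holds on the SAP's own wording. Section 13.3 counts subjects who cannot appear in the table and conflicts with Section 15.2. If any counted subject lacks a value at the time point, every cell is too small by the factor m/N and the cells sum to 100m/N percent. If none does, nothing changes.

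The adverse event point holds conditionally. If the Safety Population label sets N and subjects leave before the stage or interval, the printed incidence is m/N times that among subjects who entered or were observed. With an assumed N of 5 and one affected subject, 20.0% stands for 25.0%, 33.3% or 50.0% when 4, 3 or 2 remain. With an assumed N of 10 and one loss, it is 10.0% for 11.1%. With no attrition the figures agree. It is worth correcting because these tables carry the extension's safety summary and the correction is small.

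**What to change.** - **Shift tables (Section 13.3).** Base percentages on subjects with both a baseline value and a value at the tabulated time point. Show the number missing as a count, and state that this applies the Section 15.2 rule, so that the two sections agree.
- **Stage-specific adverse event tables (Sections 13.2 and 16.1).** Base percentages on subjects dosed at least once in that stage, or in either stage for the combined Stage 3 and 4 tables. Print that N in the column header.
- **Time to onset (Section 13.2).** For each interval, show and use the number of subjects still under adverse event observation at its start. State when observation ends for each subject, so that any event counted belongs to a subject in the denominator.
- **Optional.** Events per patient-year may be added but are not needed to correct the point.

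The cost is a few sentences in the SAP and changed denominators in the programs and shells. First and last dose dates are already on the eCRF (Section 13.1). The end of adverse event observation has to be defined, since the SAP does not do so.
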